
Rationale:

The HPV E6/E7 oncoproteins have significant roles in malignant transformation and are consistently expressed in malignant cervical tissue. Increasing levels of E6 and E7 expression cause genetic instability, and implies a risk for cellular changes, which results in a selective growth advantage (31, 34-37). The APTIMA® HPV Assay that we will be utilizing in our studies detects full-length HPV E6/E7 mRNA for HPV types 16, 18, 31, 33, 35, 39, 45, 51, 52, 56, 58, 59, 66, and 68 and correlates very well with integrated HPV, which in turn correlates with full-length HPV E6/E7 protein levels (38).

All methodologies for evaluating the expression and function of HPV E6/E7 are ongoing in the laboratory of the co-investigator ([name]) and are described in referenced publications (27-34). The expression of HPV E6/E7 proteins will be assessed by the APTIMA* HPV Assay using liquid-based cytology specimens.

Specific Aim 2 (Secondary Objective):

To quantify levels of curcumin in the cervix of women in the curcumin treatment arm.

Rationale:

To date, there are no published data on the tissue penetration of curcumin in vivo. This will establish the level of curcumin penetration in cervical tissue as well as the cumulative effect of weekly curcumin over time. This study will establish the baseline which is crucial in designing further curcumin intervention studies. The methodology of curcumin measurement for this study is well documented in Subhashini et al (16).

Specific Aim 3 (Exploratory Aim):

To determine the association between curcumin and other known biomarkers of cervical disease and its effect on the vaginal microbiome.

Rationale:

To determine the most relevant duration for curcumin treatment, as well as identify additional biomarkers that are regulated with the pharmacological activity of curcumin, we will measure mRNAand/or protein expression levels of p16INK4a, p53, Rb, VEGF and NF-κB in cervical biopsy specimens. A combination of immuno-histochemical methods and other molecular assays (RT-PCR, ELISA, TransAM NF-κB DNA binding ELISA) to determine mRNA levels and protein levels on transcription factor binding activity will also be done.

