We are proposing a prospective, randomized, two-arm, open label pilot study to demonstrate the in vivo effects previously seen in preclinical studies using cervical cancer cell lines16-20. Study participants will be recruited from the Grady Cancer Center of Excellence and the Infectious Disease Program at Grady's Ponce Clinic. A convenience sample of 40 HIV uninfected and infected participants with biopsy-proven HSIL will be randomized to one of two arms (2000 mg of curcumin powder in capsules or placebo inserted intravaginally weekly at bedtime for 12 weeks, (excluding the time when they are on their menses) as demonstrated in the schema.

Cervical cytology, vaginal swabs, colposcopies and biopsies will be performed every 4 weeks during each study visit for the study duration for the primary objectives outlined in specific aims 1-3. These time points were selected to acquire cervical samples prior to treatment, during treatment and 4 weeks after treatment completion (LEEP specimen). Study drug and placebo will be administered during weeks 1-12 (12 weeks of treatment) and no treatment will be administered during weeks 13-16 (washout period). Cervical biopsies will be performed in areas with a colposcopic suggestion of HSIL disease and four additional cervical punch biopsies (one specimen from each of four quadrants) of the cervix will be done for downstream biomarker analysis. The laboratory, pathology and data analysis staff will be blinded to treatment arm. The clinicians performing the colposcopies nor the participants will not be blinded secondary to the evident color of curcumin.

Study Population

HIV uninfected and infected women will be recruited for this study. We will focus only on HIV infected women without an AIDS defining disease, given that the risk of progression from high grade lesions to invasive carcinoma is faster in HIV infected subjects who are significantly immune compromised.

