- J. Optional: If the consent, attend a 2-3 hour focus group (maximum of 20 individuals will be selected for) at the end of the study which will be conducted by [name]. This Focus Group session aims to discuss the acceptability of the product as a treatment for pre-invasive disease using the.

Costs for this study are covered by the study and this includes the associated procedures which are covered by effort by the PI and others listed on the study.

Partners of subjects enrolled in this study

As part of the study, enrolled subjects will be given a partner notification letter informing them on the study, the purpose of this study, route of administration of the capsules, that oral sex is not permitted, and the importance of using condoms for vaginal sex whilst their partner is on the study. The notification letter will also indicate that, male partners may see a temporary discoloration and irritation on their male genetilia if a condom is not used.

Assessment of Compliance

Compliance with weekly intravaginal curcumin/placebo capsules for the duration of the study is measured by the number of nights of reported use as tabulated in the study pill diary.

Endpoints

Subjects will be monitored during the trial for disease progression, adverse events, tolerability and compliance. All study participants will undergo definitive excisional treatment (LEEP) at week 16 of the study period after a 4 weeks washout period. In addition to histology the LEEP specimens will also be tested for biomarkers and curcumin levels.

Samples:

At each visit, cervical biopsies will be divided and sent (1) to pathology for p16 staining to determine the level of dysplasia and grading/documentation of disease and (2) storage for use at a later date for research purposes only. We have designated pathologists, collaborating on this study to ensure standardization of evaluating and grading tissue and other proposed biomarkers.

SCHEDULE OF EVENTS

| Event | | | | | |
|--|--------------------|-------------------|------------------------|-------------------|--------------------|
| | Screening Visit | Baseline Visit | Study Visit Wk 4, 8 | Study Visit 12 | Study Vis Wk 16 |
| Informed Consent | * | | | | |
| Urine pregnancy test | * | * | * | * | * |
| HIV test if status is unknown* | * | | | | |
| Full physical exam | * | | | | |
| Colposcopy with Pap | * | * | * | * | * |
| Pelvic exam | | * | * | * | * |
| Vaginal sampling with colposcopy | | * | * | * | * |

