- Primary endpoints: Human papillomavirus E6/E7 (HPV E6/E7)
- Secondary endpoints: NF-κB, p16INK4a, Rb, p53 and VEGF.

HPV E6/E7 mRNA testing has been demonstrated to be a useful tool in the diagnosis of cervical cancer prevention and will be the primary end-point for this aim. The primary objective for this study is to look at the association between curcumin and cervical disease. In vitro work shows that curcumin treatment inhibits the transcription of HPV E6/E7, thus restoring the expression of proteins such as p53 and that over expression of HPV E6/E7 is a good indicator of risk and progression to cancer. (Maher DM, 2011 Jan;50(1)). Collectively the vitro and our in vivo findings may show that curcumin should be considered an effective chemopreventive and therapeutic agent for cervical cancer prevention and treatment.

Aim2: To quantify levels of curcumin in the cervix of women in the curcumin treatment arm. The mean tissue concentration of curcumin in the cervix at each time point (baseline, 1,2,3,4, and 5 months) will be calculated. This secondary objective quantifies the pharmacologically active levels of curcumin recovered from cervical tissue, for information to be gathered on the levels of curcumin that is absorbed into the cervical tissue and thus eliciting a direct pharmacological effect.

Aim 3: To determine the association between curcumin and other known biomarkers of cervical disease. This exploratory aim seeks to use repeated-measures analyses, utilizing a linear mixed model for the curcumin group to assess the association between and each biomarker (NF-kB, p16INK4a, Rb, p53 and VEGF) and the concentration of curcumin at each time point (baseline, 1, 2, 3, 4, and 5 months).

The primary analysis will be conducted with a two sample two sided t-test to compare the each of the primary endpoints and secondary endpoints, between the two arms of the study, those on treatment (curcumin capsules) and those on the placebo, respectively. If normality cannot be assumed a Wilcoxon rank-sum test will be used instead. Chi-square test or Fisher's exact test will be used to compare categorical characteristics by treatment group.

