In the secondary analyses, for the biomarker measurements, analyses of repeated measures methods are needed to properly account for the correlation between multiple observations from the same subject. Mixed-effects linear models will be employed to analyze such data while adjusting for covariates. Inference from such analyses will be limited by the small sample size of the study. However these data will provide important estimates of within-and between-subject variance that will be helpful for planning future studies. Repeated-measures analyses using mixed linear models will be performed for each biomarker outcome variable (E6/E7, p16INK4a, p53, Rb NF-kB, and VEGF). Each outcome will be analyzed with a means model with SAS Proc Mixed (version 9) providing separate estimates of the means by treatment group (curcumin and placebo) and time on study (baseline, 1,2,3,4, and 5 months). An unstructured variance-covariance form among the repeated measurements will be assumed for each outcome and estimates of the standard errors of parameters will be used to perform statistical tests and

construct 95% confidence intervals. The model-based means are unbiased with unbalanced and missing data, so long as the missing data are non- informative (missing at random). A p-value \leq 0.05 will be considered statistically significant for the main effects (treatment and time on study) and interaction term (treatment group by time on study) from the repeated measures analysis for each outcome. If there is a significant interaction effect then separate comparisons between the two treatment groups will be performed at each time point (baseline and 1,2,3,4, and 5 months). Results from these models will focus on the magnitude of the differences for each outcome. Data will be summarized using adjusted means plus 95% confidence intervals and observed differences plus 95% confidence intervals.

Additionally these biomarkers will also be quantified using immunohistochemistry methods. Immunostaining of p16 (NK4a) will be done and defined as moderate to strong diffuse or focal staining. This characterization of the staining pattern and intensity will allow one to evaluate the histological sample/biposy as having a negative, focal/patchy, or diffuse staining pattern. Generally, 100% of the low-grade and high-grade SIL's are positive for p16 staining and a strong diffuse staining with p16 suggests a high association with high-risk HPV associated lesions.

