Acceptability Questionnaires: Descriptive statistics on subject and partner responses from the acceptability questionnaires will be reported.

Power and sample size calculation: The expression of E6/7 is the primary endpoint of the study and will be used in the power and sample size calculation with a two sample two sided t-test. In this study, we will enroll 20 patients in each of the two groups. Therefore, the group sample sizes of 20 in Curcumin group and 20 in placebo group will achieve at least 80% power at the significant level of 0.05 to detect a difference of a ratio of 1.536 or higher in the expression of E6/ between the two groups, assuming the coefficent of variation is 0.5.

SAFETY EVALUATION:

Adverse Events (AEs) and Serious Adverse Events (SAEs)

This investigational agent is studied under IND # 103496 and monitoring will be performed per previously agreed upon FDA guidance.

There may be some minor irritation from the intravaginal curcumin to the vaginal mucosa and staining of underwear. Other side effects which can happen include the upset stomach, diarrhea, burning sensation in the vagina, dizziness, insomnia, rash, pruritus generalized, and fever. The literature shows that over 13 subjects in United States and 151 subjects in India (10) have been studied with curcumin without any serious adverse effects.

Our phase I study has shown that curcumin is safe in dosage up to 2000mg.

Any patient intervention related adverse effects, an unanticipated problem, or reportable protocol deviation/ non-compliance will be reported to the Emory IRB office according to IRB P & P and to the FDA according to regulations.

Any serious adverse effects will be communicated by the principal investigator to the Emory IRB using the standard adverse event reporting forms.

SAEs will be defined per FDA standards and include those that result in death, are life threatening, result in a disability, cause for hospitalization, or to a congenital abnormality or birth effect. SAEs will be reported to the DSMC, IRB and FDA and manufacturer as required.

CLINCAL OUTCOMES AND MEASURES:

The table below gives the descriptions to be used to document findings during colposcopy.

| Colposcopic findings | | | | Presence | |
|----------------------|----------------------|----------------------|----------------------|----------|--------|
| | Grade 1 | Grade 2 | Grade 3 | | |
| | (Mild) | (Moderate) | (Severe) | Present | Absent |

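### The primary E6/E7 t-test names no visit and leaves the planned pre-treatment value unused; naming one visit and adjusting for baseline would make the result interpretable and probably more precise at almost no cost

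*Combined protocol and SAP*

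**What the plan says.** The primary-analysis paragraph of STATISTICAL ANALYSIS (after Aim 3) reads: "The primary analysis will be conducted with a two sample two sided t-test to compare the each of the primary endpoints and secondary endpoints". The fallback is equally brief: "If normality cannot be assumed a Wilcoxon rank-sum test will be used instead". Neither names a visit, a change from baseline or a covariate. The Aim 1 text defines the outcome only as a level in the collected samples. The power paragraph says that 20 women per arm "will achieve at least 80% power at the significant level of 0.05 to detect a difference of a ratio of 1.536 or higher", assuming a coefficient of variation of 0.5, and it too gives no time point.

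Several values per woman are planned. RESEARCH DESIGN AND METHODS says: "Cervical cytology, vaginal swabs, colposcopies and biopsies will be performed every 4 weeks during each study visit for the study duration". E6/E7 is to be measured "using liquid-based cytology specimens" (Specific Aim 1, Rationale). Study product is given in weeks 1 to 12, and "no treatment will be administered during weeks 13-16 (washout period" applies after that. Under Endpoints: "All study participants will undergo definitive excisional treatment (LEEP) at week 16 of the study period after a 4 weeks washout period".

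Baseline appears only in the secondary mixed model, as one level of time, "providing separate estimates of the means by treatment group (curcumin and placebo) and time on study (baseline, 1,2,3,4, and 5 months". That model is said to adjust for covariates, but none is named. It also lists months 1 to 5, whereas the SCHEDULE OF EVENTS ends at week 16.

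**The concern.** A two-sample t-test takes one value per woman. Each woman is due to supply four after baseline: three on treatment and one after washout. The primary test therefore cannot be run until someone makes a choice that the plan does not make.

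The choice changes the question. Week 12 estimates the effect at the end of exposure; week 16 estimates what persists four weeks later. A reader given only a ratio and a p-value could not tell which had been measured. An unnamed visit also leaves room to choose after the data are seen, although nothing in the documents says that this will happen. The month labels add to the uncertainty, because a month 5 value has no scheduled visit.

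The second issue is efficiency. A pre-treatment value is planned for every woman, and the primary test ignores it. With 20 per arm, any useful correlation between baseline and follow-up would narrow the confidence interval using data already being collected.

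**Working it through.** **Inputs from the plan** (Power and sample size calculation): 20 per arm, two-sided 0.05, ratio 1.536, coefficient of variation 0.5. **Assumed, because the documents do not give them:** the baseline to follow-up correlation ρ, the correlation between visits, and the share of effect retained after washout.

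**1. The plan's own figure.** On the log scale:

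- SD = √ln(1 + 0.5²) = 0.4724
- effect = ln(1.536) = 0.4292
- noncentrality = 0.4292 / (0.4724 × √(2/20)) = 2.873, with 38 df
- power = 0.7995; the ratio detectable at exactly 80% is 1.5364

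The stated power reproduces. Alternatives do not fit: the raw scale with SD 0.5 and difference 0.536 gives 0.910, and a log SD of 0.5 gives 0.753. The trial was therefore powered as an unadjusted, log-scale comparison at a single time point, and that time point is never named.

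**2. Adding log baseline as a covariate.** Residual SD = 0.4724 × √(1 − ρ²), with 37 df. The variance is multiplied by 1 + 1/36 to allow for chance baseline imbalance. At ρ = 0.5, for example, the SD is 0.4091 × √(37/36) = 0.4147, the noncentrality is 0.4292 / (0.4147 × √(2/20)) = 3.27, and power is 0.890.

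| Assumed ρ | Power, formula | Power, simulated (200,000 trials) | Ratio detectable at 80% power |
|---|---|---|---|
| Unadjusted t-test | 0.7995 | – | 1.536 |
| 0 | 0.788 | 0.787 | 1.546 |
| 0.3 | 0.825 | 0.824 | 1.515 |
| 0.5 | 0.890 | 0.890 | 1.458 |
| 0.7 | 0.972 | 0.971 | 1.365 |

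Break-even is at ρ of about 0.17. A simple change score is not a substitute: its SD is 0.4724 × √(2(1 − ρ)), so at ρ = 0.3 its power is only 0.658, and it merely equals the unadjusted test at ρ = 0.5.

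**3. How much the visit could matter (illustration only).** If 75% or 50% of the log effect remained after washout, the planned t-test at week 16 would have noncentrality 2.155 or 1.437 and power 0.56 or 0.29, against 0.80 at full effect.

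**4. Worst case for an unnamed visit.** These are false-positive rates from 200,000 simulated null trials, 20 per arm, if the best visit were claimed at 0.05:

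| Correlation between visits | Best of four visits | Better of weeks 12 and 16 |
|---|---|---|
| 0.3 | 17.5% | 9.5% |
| 0.5 | 15.8% | 9.1% |
| 0.7 | 13.2% | 8.5% |

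**The case against.** The strongest reply is that baseline adjustment is a preference and not a correction. The t-test is unbiased at a fixed visit, its power is correctly stated, and this is a 40-woman pilot whose authors say that inference from the repeated-measures analyses is limited by sample size. The gain depends wholly on an unknown correlation. All of that stands, and it is why the second part of the point is about precision only.

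The cost may also exceed one degree of freedom. Covariance analysis needs a usable quantitative value at both times, and eligibility rests on HSIL cytology, not on detectable E6/E7. If two women per arm were dropped for lack of a usable baseline, power at ρ = 0.3 would be 0.780, below the unadjusted test on all 40. A repeated-measures model with a common baseline mean avoids that loss by keeping those women. If the assay gave only detected or not detected, the figures above would not apply. However, the plan treats E6/E7 as a level with a coefficient of variation, and a visit would have to be named in either case.

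The best-of-four figures describe a procedure that the plan does not contain. Its only written per-visit comparisons are in the secondary model and require a significant treatment-by-time interaction first. Simulated with complete data, that gate lets a false per-visit claim through in about 1.6% to 3.1% of null trials. This is reassuring for the secondary model but does not bind the primary t-test.

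Nor does the mixed model fill the gap. It is secondary and names no primary visit. With separate arm means at every time, its contrast at a given visit with complete data is just the raw difference in means, with no baseline adjustment.

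On the month labels, Treatment Plan does speak of a four-to-five-month course, and the study schema was not available for this check. The written schedule still ends at week 16.

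**Conclusion.** The concern holds on both counts. The missing visit is the more important one: it depends on no assumption, and it leaves the primary result undefined between an on-treatment effect and persistence after washout.

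The unused baseline is a loss of precision, not of validity. Adjustment is worth about 2.5 points of power at a correlation of 0.3, about 9 at 0.5 and about 17 at 0.7, and it costs about 1 point at zero. These figures assume a quantitative E6/E7 value that can be logged, roughly log-normal, in all 40 women at both times. The washout powers and the multiple-visit error rates show what could be at stake; they are not estimates of what will happen. The sample size itself is not in question. The change should be made before any outcome data are examined by arm.

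**What to change.** - Name one primary visit for E6/E7 and say why. Week 12 fits the hypothesis that curcumin lowers expression; week 16 tests persistence. The choice is the sponsor's. Make the other visits secondary.
- At that visit, make the primary analysis a covariance analysis of log E6/E7 with arm as factor and log baseline E6/E7 as covariate. Alternatively, take that visit's contrast from a repeated-measures model with baseline as covariate or with a common baseline mean. Report the geometric mean ratio with its 95% confidence interval.
- State which pre-treatment specimen is the baseline. The schedule table lists a Pap at both screening and baseline, while the visit narrative mentions it only at screening.
- Confirm that the assay result is quantitative, and pre-specify how undetectable values are handled, since their log is undefined. Replace the unadjusted Wilcoxon fallback with a rank-based, baseline-adjusted one.
- Reconcile months 1 to 5 in the statistical section with the schedule that ends at week 16.

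The cost is analysis-plan wording, a rule for undetectable values and one degree of freedom. No extra samples, visits or participants are needed.

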Enrolled subjects will be asked to agree to the use of reliable birth control: Combined oral contraceptive pill (OCP), Long Lasting Reversible Contraceptive (LARCP), Bi-Lateral Tubal Ligation (BLT) and Depo-Provera Shot/Birth control shot and they will be given a partner notification letter advising them to use a condom when having vaginal sex with their partner and the risks associated with lack of use of a condom.

Clinical care practice guidelines indicate colposcopy every 6 months. We will be following these subjects every month with colposcopy for research purposes of this study, which is more than sufficient to clinically monitor and capture any women at risk for progression of disease. Subjects will be informed that the alternative to this study or if disease progression occurs, is referral for continued clinical care with their provider where they will this they will discuss the treatment (Leep with continued active monitoring-colposcopy with biospies) with their provider at the Grady Cancer Center of Excellence treatment Clinic or at the Emory Clinic.

Randomization Method

The treatment assignments will be generated with the use of a pseudo-random-number generator with randomly permutated blocks that will be used to ensure balance between the number of subjects assigned to each treatment (1st: 2000 mg of curcumin for 12 weeks versus placebo capsules for 12 weeks). Before the study starts, the Pharmacist at Ponce Clinic (IDP) or Grady CRN will be sent a batch of sealed, sequenced, opaque envelopes containing the treatment assignment. The envelopes will have a unique ID consisting of a sequence number determining the treatment arm. Once informed consent is obtained on a subject, the Study Coordinator/P.I. will set up an appointment for the screening visit at the Ponce clinic (IDP) or Grady CRN to confirm clinical eligibility. Once the participant is cleared to enter the study, they will be given a unique ID associated to the batch of envelopes in the care of the Grady CRN or Ponce Clinic (IDP) Pharmacist.

Subject Recruitment:

All subjects will be recruited from Grady Cancer Center of Excellence at Grady Memorial Hospital (GMH) and the Grady Infectious Disease clinic at Ponce (IDP) per the inclusion and the exclusion criteria below.

Inclusion Criteria:

- 1. Age 21 years and older
- 2. HIV uninfected and infected women (without AIDS defining illness)
- 3. HSIL cytology with no invasive features identified on colposcopy or the baseline biopsy

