| Targeted cervical biopsies | | * | * | * | * |
| 30 day supply of medication (curcumin/placebo) | | * | * | | |
| Pill diary review | | | * | * | * |
| Partner notification letter (distribution) | * | | | | |
| Leep Procedure | | | | | * |

All subjects will be asked to complete an acceptability questionnaire at the end of the study. Focus group: 20 subjects will be invited to attend a focus group to discuss the acceptability of the medication. *HIV test will not be performed if there is a negative test documented in the medical records 3 months prior to screening visit.

SCHEDULE OF EVENTS

Screening Visit

Screening evaluations will determine eligibility and will occur prior to the participants' enrollment into the study. At the screening visit subjects will have:

- A urine test to see if they are pregnant.
- HIV status will be confirmed based on medical records or testing during the screening visit
- They will be asked to agree to the use of reliable birth control: Combined oral contraceptive pill (OCP), Long Lasting Reversible Contraceptive (LARCP), Bi-Lateral Tubal Ligation (BLT) and Depo-Provera Shot/Birth control shot.
- They will be given a partner notification letter about the study.
- A full physical exam will be done.
- A colposcopy with Pap smear to check for the presence of human papilloma virus; vaginal sampling for infection and microbiome to get a baseline state of the vagina.

Study Visits

Baseline and all other study visits will occur after the screening visit.

Baseline:

- Urine test to see if they are pregnant.
- A pelvic exam will be done.
- Vaginal sampling and colposcopy with targeted cervical biopsies will be done.
- They will be given a pill diary and a 4-week supply of the study medication (curcumin or placebo).
- Instruction on insertion of the intravaginal capsules will be given and they will be reminded of potential side effects of the medication.
- They will be asked to return for another study visit 4 weeks later.

Study visits wk 4 and wk 8:

- Urine test to see if they are pregnant.
- A pelvic exam.
- Vaginal sampling and colposcopy with targeted cervical biopsies.
- Their pill diary will be reviewed (aspects of time, frequency and date of distribution of the medication)
- They will be given another 4-week supply of the study medication (curcumin or placebo).
- They will receive a phone call twice a week to address any issues.
- They will be asked to return for another study visit 4 weeks later.

Study visits wk 12:

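### Entry rules conflict on biopsy-proven versus cytologic HSIL, and capsules are dispensed at the visit where the first scheduled biopsy is taken, with no wait for its report

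*Combined protocol and SAP*

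**What the plan says.** Four parts of the combined protocol and SAP bear on who enters and when.

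- **Research Design and Methods** describes 40 women and says that "participants with biopsy-proven HSIL will be randomized to one of two arms". Specific Aim 1 concerns E6/E7 mRNA within HSIL lesions; it does not itself require biopsy proof.
- **Inclusion Criteria**, item 3, requires "HSIL cytology with no invasive features identified on colposcopy or the baseline biopsy". The biopsy serves there only to rule out invasion. No inclusion or exclusion item asks for HSIL on histology.
- **Randomization Method** says: "Once the participant is cleared to enter the study, they will be given a unique ID associated to the batch of envelopes" held by the pharmacist. The screening visit is where clinical eligibility is confirmed.
- **Schedule of Events** says: "Screening evaluations will determine eligibility and will occur prior to the" participant's enrolment. Neither the screening column of the table nor the screening list contains a biopsy. The baseline list says "Vaginal sampling and colposcopy with targeted cervical biopsies will be done", and the same list hands out the first month of capsules. Under Samples, "cervical biopsies will be divided and sent (1) to pathology for p16 staining to determine the level of dysplasia".

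On the analysis, the Statistical Analysis section says "The primary analysis will be conducted with a two sample two sided t-test to compare the each of the primary endpoints"; the comparison is of one arm with the other, and it covers the secondary endpoints too. The power paragraph counts 20 women in each arm.

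**The concern.** The design section and the inclusion criterion admit different women. Whichever is meant, the result needed to apply it comes from tissue taken at the visit where treatment starts. Two kinds of woman can slip through. One has HSIL cytology but no HSIL on the baseline biopsy: she satisfies the criterion and not the design statement. The other has invasion on that biopsy: she is ineligible, but this may be learned only after she has been allocated and given capsules.

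The second case is a safety matter. The first means that the 40 women may not all belong to the population that the trial says it studies. E6/E7 is measured on liquid-based cytology, so an unconfirmed woman would still have a primary endpoint value, and the plan does not say in words that she stays in.

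**Working it through.** **Order of events, as written**

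1. Screening: pregnancy test, HIV status, contraception, partner letter, physical examination, colposcopy with Pap, vaginal sampling. No biopsy.
2. Clearance, then an ID linked to a sealed envelope.
3. Baseline visit: biopsy taken and capsules supplied. The capsules are arm-specific, so allocation is settled by the end of this visit.
4. The biopsy goes to pathology for grading. No turnaround time and no hold on dispensing are stated.

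| Baseline biopsy | Design section | Inclusion 3 | Position when the report arrives |
|---|---|---|---|
| HSIL, no invasion | met | met | correctly entered |
| No HSIL | not met, unless an earlier biopsy showed it | met | may be randomised and hold capsules |
| Invasion | not addressed | not met (exclusion 2 also concerns invasion) | may be randomised and hold capsules |

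**The plan's own power figure**

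Inputs from the power paragraph: 20 per arm, ratio 1.536, coefficient of variation 0.5, two-sided 0.05.

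- Log-scale SD = √ln(1 + 0.5²) = 0.4724
- Log effect δ = ln 1.536 = 0.4292
- Standard error = 0.4724 × √(2/20) = 0.1494; noncentrality = 0.4292 / 0.1494 = 2.87
- Noncentral t, 38 df: power 0.7995

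The stated 80% is reproduced. It counts all 40 women and gives each the full effect.

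**What unconfirmed women could cost**

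Let f be the share without HSIL on the baseline biopsy. The documents give no value, so 10%, 20% and 30% are assumptions.

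- Excluded: 20(1 − f) women per arm, same effect.
- Kept, no curcumin effect in them, same E6/E7 level: mean log difference (1 − f)δ, pooled SD √(0.4724² + f(1 − f)δ²/2).
- Kept, same effect in them: nothing changes.

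| f | Excluded: n per arm, power | Kept, no effect: difference, SD, power | Kept, same effect |
|---|---|---|---|
| 10% | 18, 0.754 | 0.386, 0.481, 0.697 | 0.80 |
| 20% | 16, 0.701 | 0.343, 0.488, 0.583 | 0.80 |
| 30% | 14, 0.638 | 0.300, 0.492, 0.468 | 0.80 |

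A simulation of 100,000 trials per setting, with the number of unconfirmed women left to chance, gives 0.753, 0.696 and 0.634 for the excluded column.

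**Numbers needed**

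Waiting for the report means biopsying about 40/(1 − f) women to randomise 40: 44.4, 50 and 57.1, so 45, 50 and 58. Randomising first and replacing later needs 20/(1 − f) per arm: 23, 25 and 29.

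**The case against.** The best defence is that the criteria already forbid this. Criterion 3 and exclusion 2 both depend on a biopsy, and an envelope is released only for a woman who has been cleared. A woman whose biopsy is unreported cannot properly be cleared. That reading is sensible, but the schedule does not carry it out, because it supplies capsules at the visit where the biopsy is taken. The conflict remains for site staff to resolve.

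Second, the schedule is not a full list of eligibility evidence. CD4 count, viral load and endocervical curettage are required and do not appear in it. Records are reviewed at screening and women come from specialist clinics, so many may arrive with a biopsy. The schema figure is also not available in the text read. This stands as a limit on how often the problem would occur. It does not remove it, since no criterion requires an earlier biopsy and criterion 3 names the baseline one.

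Third, the endpoint is measured on cytology specimens, and a targeted biopsy can miss a lesion. A negative biopsy does not show that curcumin has nothing to act on. This stands, and it is why the range for keeping such women runs up to 0.80.

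A reader might go further and infer that the plan sets up two analysis populations, and so two competing primary tests with a lost 5% error rate. The documents do not support that. The two HSIL descriptions concern entry. The primary test compares the two arms, the power counts 20 in each, and nothing provides for removing or replacing a randomised woman. Data analysis staff are blinded. Inflation would need someone to run both tests and report the better one after unblinding, which the plan does not propose.

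**Conclusion.** The entry texts contradict each other, and the schedule defeats the one safeguard that inclusion 3 places on the biopsy. Followed as written, the plan can randomise and supply capsules to a woman who lacks histologic HSIL or whose biopsy then shows invasion. This rests on the written criteria and visit lists, and on pathology not reporting within the baseline visit itself.

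The size cannot be fixed from the documents. The ranges worked out above rest on an assumed share of 10–30%, and the lower end for keeping unconfirmed women (0.47) further assumes no effect in them and the same E6/E7 level. A reader might infer that the 80% power is wrong; it is not. Nor is the t-test at fault. This is a correction to eligibility and sequence, and it should be made because it is cheap and protects participants.

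**What to change.** 1. **Inclusion Criteria, item 3:** change to *biopsy-proven HSIL with no invasive features*, matching Research Design and Methods. If entry on cytology is really intended, the design section must change instead; the hold in item 2 is needed either way, because invasion is judged on the biopsy.
2. **Randomization Method and Schedule of Events:** add *Randomisation and the first dispensing take place only after pathology has reported HSIL without invasion, on either a clinic biopsy within a stated recent window or the scheduled baseline biopsy.* No biopsy is added. Where the baseline biopsy is used, capsules are released once the report is in, and study weeks are counted from that release.
3. **Statistical Analysis:** add *All randomised women are analysed in their assigned arm.* This confirms the natural reading of the section.

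The cost is a short wait for one pathology report, and some women found ineligible before randomisation instead of after it. The Treatment Plan sees no concern about CIN 3 progression over the 4–5 months of the study, so the wait is acceptable on the plan's own terms. The gain is that all 40 women fit the stated population and none with invasion on the entry biopsy is dosed.
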